## **ABSTRACT.**

**Background:** Percutaneous electrotherapy is today a therapeutic alternative in musculoskeletal conditions. In that sense, percutaneous microelectrolysis (MEP) stands out as treatment for tendinopathies and musculoskeletal pain, such as myofascial trigger points (MTrPs), although more studies are needed to support it.

**Objective:** Investigate effectiveness of MEP in reducing painful pressure threshold (PPT) and pain intensity (PI) in MTrPs.

**Method:** Controlled randomized clinical trial. Research was performed at Physiotherapy Laboratory of Andrés Bello University. Participants were forty-eight volunteers with MTrPs presence in upper trapezius muscle. Both groups received a baseline ultrasound treatment, adding MEP to experimental group. Intervention consisted of a MEP intervention and tree

reevaluation sessions (at day one, three and seven). Direct current was delivered with acupuncture needle directly to MTrP and PPT and PI was reevaluated before and after application. Main outcomes were PPT and PI differences (PPTdiff and PIdiff) between evaluation sessions.

**Results:** MEP demonstrated positive changes increasing PPT (PPTdiff1-1, p=0,0000, PPTdiff2-1, p=0,0000, PPTdiff3-1, p=0,0000) and decreasing PI (PIdiff1-1, p=0,0001, PIdiff2-1, p=0,0001, PIdiff3-1, p=0,0008) in experimental group, and significant differences in PPT at second reevaluation session compared to control group (PPTdiff2-1, p=0,0032).

**Conclusion:** MEP is a good analgesic treatment for MTrPs compared to therapeutic ultrasound, although neither of two therapies seems to be better than other in long term. Two treatments improvements PPT and PI, so MEP can be considered as an effective alternative treatment for MTrPs pain.

**Keywords:** electrotherapy; electrolysis; pain threshold; myofascial pain syndromes; analog visual scale.

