### 4. Therapeutic ultrasound application.

Participants of both groups received a therapeutic ultrasound treatment. Experimental group received first ultrasound and subsequently MEP, while control group was treated only with ultrasound. Ultrasound intervention protocol was performed in the same way for both groups. Application was performed in an adjoining room by another physiotherapist who didn't know

groups. Treatment was carried out with participant in sitting position applying ultrasound at sensitive point marked by examiner of evaluation station. Ultrasound therapy was delivery at 1MHz, 1.5 Watts/cm^2, 100% duty cycle (SATP: 1.5Watts/cm^2 and SATA:1.5W/cm^2), ERA 5cm^2 and 15 minutes. Once ultrasound intervention was finished, participants of MEP group were taken to microelectrolysis box, while participants of control group returned to evaluation station.

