##### 6. Pain pressure threshold (PPTpre) and pain intensity (PIpre) postintervention evaluation.

Completing intervention, participants returned to evaluation station. Evaluator repeated the same assessment protocol made before ultrasound and MEP application, recording PPT and PI postintervention. Variables PPTdiff1-1 and PIdiff1-1 were created based on differences

between algometry and pain intensity measurements before and after intervention. Participants were cited for a reevaluation on day three and seven obtained variables PPT2, PI2, PPT3 and PI3. This allowed to create PPTdiff2-1, PPT3-1, PI diff2-1 and PI diff3-1 variables, that represented differences obtained between the measurements of days three and seven with those obtained on day one before intervention.

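### The six experimental-arm p-values that the abstract credits to MEP are changes after ultrasound plus MEP; only the between-arm comparisons speak to MEP.

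*Protocol*

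**What the plan says.** The Abstract (Method) explains that both groups had ultrasound and that MEP was added in one. It then describes the measurements: "Direct current was delivered with acupuncture needle directly to MTrP and PPT and PI was reevaluated before and after application". Its Results give six p-values in the experimental group under the statement that "MEP demonstrated positive changes increasing PPT" and lowered PI: 0,0000 for each of PPTdiff1-1, 2-1 and 3-1, and 0,0001, 0,0001 and 0,0008 for the matching PI differences. One between-arm result follows: "significant differences in PPT at second reevaluation session compared to control group", p=0,0032.

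The Procedure gives the day-one order. The pre reading is taken at the evaluation station (section 3). Then "Experimental group received first ultrasound and subsequently MEP, while control group was treated only with ultrasound" (section 4). The next step differs by arm: "Once ultrasound intervention was finished, participants of MEP group were taken to microelectrolysis box, while participants of control group returned to evaluation station". After MEP (section 5), "Evaluator repeated the same assessment protocol made before ultrasound and MEP application, recording PPT and PI postintervention" (section 6).

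Section 6 builds the day-one differences from the pre and post readings: "Variables PPTdiff1-1 and PIdiff1-1 were created based on differences". The later differences compare "measurements of days three and seven with those obtained on day one before intervention". All six difference variables therefore start from the one reading before ultrasound.

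**The concern.** Someone who reads only the Abstract will take the six p-values as changes across the direct current, because the current is the only application named in that sentence. They are changes across the whole session. The Abstract's own conclusion says that PPT and PI improved under both treatments, so by its own account the non-MEP part of the change is not negligible.

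What is at stake is the conclusion that MEP is an effective analgesic alternative. Of the seven p-values in the Abstract's Results, six are of the within-arm kind and one compares the arms. If the six do not bear on MEP, the conclusion rests on the one.

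**Working it through.** **1. Order of events on day one (Procedure, sections 3 to 6)**

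| Step | MEP arm (n = 24) | Control arm (n = 24) |
|---|---|---|
| 1 | PPT and PI read (pre) | PPT and PI read (pre) |
| 2 | Ultrasound, 15 minutes | Ultrasound, 15 minutes |
| 3 | Straight to MEP, no reading | Back to the evaluation station |
| 4 | MEP | none |
| 5 | PPT and PI read (post) | PPT and PI read (post), directly after step 2 |

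No reading in the MEP arm falls between steps 2 and 4.

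**2. What each quantity estimates.** Let U be the mean ultrasound response, M the mean response to adding MEP, and T the mean change from time, retest and other non-specific causes.

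- MEP-arm change = U + M + T
- Control-arm change = U + T
- Difference between arms = (U + M + T) − (U + T) = M, if the effects are additive

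A within-arm test asks whether U + M + T = 0. It can reject with M = 0. The between-arm difference does bear on M, although M here includes any non-specific effect of being needled.

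**3. Could p-values of this size arise without any MEP effect?** The test behind them is not stated, so assume a paired t-test with n = 24 (23 df). The mean change in units of its own SD is then t/√24.

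- p = 0.0008: t = 3.86, and 3.86/4.90 = 0.79
- p = 0.0001: t = 4.69, and 4.69/4.90 = 0.96
- printed 0,0000, so below 0.00005: t above 4.97, and 4.97/4.90 = 1.01

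A shared change U + T of about 0.8 to 1.0 SD would produce all six results with M = 0. This does not show that M is zero. It shows that the six p-values do not distinguish M from U + T. The Protocol prints no change-score means or SDs, so the split cannot be estimated.

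**4. What remains for MEP.** Two outcomes at three time points give 2 × 3 = 6 between-arm comparisons. The Abstract names one as significant, so 6 − 1 = 5 are not named.

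**5. What adjusting for the existing pre reading could gain.** The variances are not printed, so this is an illustration. Take pre = P + e0 and outcome = P + ρ·R + e2. P is a person's stable level (SD 1) and R a person's ultrasound response (SD 0.35 to 1.0). The reading errors e0 and e2 have SD s = 0.7 to 1.0, and ρ is the share of R that persists (0, 0.5 or 1).

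- Variance of the plain difference: ρ²·SD(R)² + 2s²
- Variance adjusted for the pre reading: 1 + ρ²·SD(R)² + s² − 1/(1 + s²)

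Smallest gain (s = 0.7, SD(R) = 1, ρ = 1): plain 1 + 0.98 = 1.98; adjusted 1 + 1 + 0.49 − 1/1.49 = 1.82; reduction 8%. Largest gain (s = 1, ρ = 0): plain 2.00; adjusted 1 + 1 − 0.5 = 1.50; reduction 25%. Over this grid, adjustment lowers the variance by 8% to 25% with no new measurement.

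**The case against.** The strongest reply is that this is a randomised add-on trial, and a baseline taken before any study treatment is the usual and valid choice. The shared ultrasound response cancels between arms, so the difference variables are fit for purpose. That stands. A reader might infer that all six variables start too early and that the comparison with control is therefore biased. The documents do not support this: both arms have the same baseline and the same ultrasound, and under additivity the difference estimates the effect of adding MEP. One limit applies to day one only. Controls are read directly after ultrasound and MEP participants later, by two 30-second pauses plus three emission times whose lengths are not given, so cancellation there may be imperfect.

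A reader might also see a flat contradiction between the Abstract and the Procedure. That goes too far. The pre reading is before the current and the post reading after it, Material and Methods refers to the intervention as a whole, and section 6 is explicit about the order. The Abstract's sentence is loose and misleading, not false.

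Finally, a reader might conclude that the trial needed a reading between ultrasound and MEP. Such a reading could improve precision, but the gain depends on variance components that the Protocol does not give. A change from that reading within the MEP arm would still include repeat-press and time effects, so the control arm would still be needed. It also cannot be added to a trial that already reports results.

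None of this rescues the attribution of six within-arm changes to MEP.

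**Conclusion.** The point holds as one of attribution. All six experimental-arm p-values in the Abstract describe change after ultrasound plus MEP, with time and retest effects included, and none of them can show an effect of MEP. The evidence on MEP is the between-arm comparison, where one of six contrasts is named as significant. That the shared ultrasound does not bias this comparison rests on additivity and, on day one, on the later reading in the MEP arm making little difference. The share of the within-arm change due to MEP is unknown. This changes what the trial may conclude, because the statement that MEP is an effective treatment leans on those six results.

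**What to change.** 1. In the Abstract (Method), state that PPT and PI were read before ultrasound and after the complete intervention, and that no reading was taken between ultrasound and MEP.
2. In the Abstract (Results), label the six experimental-arm p-values as changes after ultrasound plus MEP.
3. Base every conclusion about MEP on the between-arm comparison at each time point, for PPT and for PI, and word it as the effect of adding MEP to ultrasound. Report all six comparisons.
4. Adjust each comparison for the pre-intervention value of the same outcome, which is already collected. If a statistical analysis plan exists and already does this, only the wording changes remain.

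The cost is a few sentences and a re-analysis of existing data. The downside is that the evidence for MEP becomes less favourable, since only PPTdiff2-1 (p=0,0032) is reported as significant between arms.

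A post-ultrasound reading is an option for a future study only. Controls would then need a wait matched to the MEP time and a second reading to serve as their outcome, so the cost is more than one extra press.

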## **Material and Methods**

Present design represents a randomized double-blind clinical trial. Study was approved on June 18, 2019 by Eastern Metropolitan Health Service of Santiago (SSMO) ethics committee. Study was registered at [www.clinicaltrials.gov](http://www.clinicaltrials.gov). Participants were divided in two groups assessed in both presences of MTrPS in shorter upper trapezius muscle. It was recording the PPT and PI before and after intervention. Both groups received therapeutic ultrasound as baseline treatment. Experimental group received microelectrolysis additionally. A reassessment of PPT and PI was done on day one, three and seven post intervention.

*Subjects.* forty-eight healthy volunteers were recruited (23 men, 25 women, average age 22 years). Participants were students of Science Rehabilitation Faculty (SRF) of Andrés Bello University, Santiago de Chile. Number of participants was selected by convenience. An invitation was extended to students through formal communication channels (mailing), student representatives and social networks, summoning two hundred and seven potential participants. Selection was based on a survey whose first part was structured in relation to general demographic participant's data, including name, age, sex, body mass index (BMI), career year, and personal information contact (e-mail and cell phone number). Second part of survey consisted of closed questions constructed by eligibility criteria. Inclusion criteria considered participants over 18 years old, students of SRF and positive hypersensitive MTrPs. Exclusion criteria include neck or shoulders pathologies in the last 6 months (as fractures, sprains, tendinopathies, dislocations or muscle tears), cervical pain, sensitivity alterations such as hypesthesia, anesthesia or hyperesthesia in neck, shoulders and/or arms, wounds or skin alterations in shoulder as psoriasis, scars or keloids, fear to electrotherapy application and analgesic pharmacological treatment at recruitment time (non-steroidal anti-

inflammatory or steroidal drugs). Elimination criteria considered non-tolerance electrotherapy intervention and non-completion of evaluation protocol (attendance at all scheduled sessions). Demographic data were tabulated in Microsoft excel® 2016 program (Table 1, characterization of study groups).

Variable	MEP (n = 24)	Control (n = 24)	p-value	Sample distribution

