**Figure 1. Subject recruitment and flow through the study**

## 2. Groups.

Sample was divided by a simple randomization process performed with a random number table, assigned participants to one of two study groups. Sequence of randomization and participants of each group was only known by principal investigator. Working groups were designated as experimental (MEP group, n = 24) and control group (n = 24). None subjects knew the treatment that would be applied. Each participant was evaluated registering their age, BMI and SUTL. Location of MTrP was determined at shortness trapezius muscle, taking as reference a line between superior acromion's midpoint surface and C7 spinous process (PE-AC distance). Algometry and VAS was subsequently applied obtaining the PPT and PI

pre intervention (PPTpre y PIpre). Variables described were compared between groups to assess the homogeneity of them (Table 1). Data reflect the homogeneity of groups at the beginning of the study.

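### Optional precision gain: the six main outcomes use baseline PPT or PI only by subtraction; adding that baseline as a covariate may narrow the between-arm intervals

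*Protocol*

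**What the plan says.** The Abstract names the main outcomes: "Main outcomes were PPT and PI differences" between evaluation sessions. Section 6 of the Procedure defines them. For day one, "Variables PPTdiff1-1 and PIdiff1-1 were created based on differences" between the measurements before and after the intervention. The later variables are described as ones "that represented differences obtained between the measurements of days three and seven with those obtained on day one before intervention". That makes six outcomes: three differences for PPT and three for PI, all sharing the same day-one baseline.

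The Abstract reports a between-arm result on one of them, "significant differences in PPT at second reevaluation session compared to control group" (PPTdiff2-1, p = 0.0032), and concludes that "neither of two therapies seems to be better than other in long term". The only other stated use of baseline PPT and PI is the comparison of groups at entry in Table 1. On sample size, Material and Methods says "Number of participants was selected by convenience". The groups are 24 and 24.

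**The concern.** A raw difference gives the baseline a fixed coefficient of 1. If the true slope of follow-up on baseline is not 1, the difference carries variance that a fitted slope would remove. The sample size was not chosen for precision and recruitment is over, so any further precision must come from the analysis. The baselines have already been measured on every participant. At stake is the width of the between-arm intervals for six outcomes, and nothing more.

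**Working it through.** **Nothing to reproduce.** The Protocol gives no power, alpha or precision calculation. As an input check, a two-sample t-test on the printed PI baselines (32.1, SD 13.6, and 31.4, SD 15.1, 24 per arm) gives p = 0.867 against the printed 0.8729. Rounding of the printed values allows 0.847 to 0.886, so the inputs are consistent.

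**Inputs from the Protocol.** N = 48, 24 per arm (Procedure, section 2). Baseline PI SD, pooled from Table 1: sqrt((13.6² + 15.1²)/2) = 14.37 mm. Baseline PPT SD: 0.2 kg/cm² in both arms, a rounded figure (0.15 to 0.25), so the PPT results below could scale by ±25%.

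**Assumed, because not given.** The correlation rho between baseline and follow-up, the ratio k of follow-up SD to baseline SD, and that all 48 participants are analysed.

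**Variance per participant**, with baseline SD s:
- raw difference: s²(1 + k² − 2k·rho)
- baseline-adjusted: s²k²(1 − rho²)
- the first minus the second: s²(1 − k·rho)², which is never negative and is zero when the slope k·rho equals 1.

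**Cost of fitting the slope.** The expected variance is multiplied by 1 + 1/(48 − 4) = 1.0227. One degree of freedom is lost (46 to 45), which moves the 95% critical value from 2.0129 to 2.0141.

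**Net SE reduction** = 1 − sqrt(ratio × 1.0227), where ratio = k²(1 − rho²)/(k² + 1 − 2k·rho):

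| k | quantity | rho 0.3 | rho 0.5 | rho 0.7 | rho 0.9 |
|---|---|---|---|---|---|
| 1 | ratio | 0.650 | 0.750 | 0.850 | 0.950 |
| 1 | net SE reduction | 18.5% | 12.4% | 6.8% | 1.4% |
| 1.5 | ratio | 0.871 | 0.964 | 0.998 | 0.777 |
| 1.5 | net SE reduction | 5.6% | 0.7% | −1.0% | 10.8% |
| 2 | ratio | 0.958 | 1.000 | 0.927 | 0.543 |
| 2 | net SE reduction | 1.0% | −1.1% | 2.6% | 25.5% |

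Simulation at 24 per arm (40,000 trials per cell) agrees to within 0.7 percentage points. Its worst point, k = 1.5 with rho = 2/3 (slope exactly 1), is a loss of 1.2%. In a separate simulation of 20,000 trials per setting, type I error was 0.047 to 0.052 for both analyses.

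**95% CI half-widths.** Unadjusted: 2.0129 × s × sqrt(k² + 1 − 2k·rho) × sqrt(2/24). Adjusted: 2.0141 × s × k × sqrt(1 − rho²) × sqrt(2/24 × 1.0227). Each cell shows unadjusted, then adjusted:

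| Outcome, k | rho 0.3 | rho 0.5 | rho 0.7 | rho 0.9 |
|---|---|---|---|---|
| PI (mm), 1 | 9.9, 8.1 | 8.3, 7.3 | 6.5, 6.0 | 3.7, 3.7 |
| PI (mm), 2 | 16.3, 16.1 | 14.5, 14.6 | 12.4, 12.1 | 9.9, 7.4 |
| PPT (kg/cm²), 1 | 0.138, 0.112 | 0.116, 0.102 | 0.090, 0.084 | 0.052, 0.051 |
| PPT (kg/cm²), 2 | 0.227, 0.224 | 0.201, 0.204 | 0.172, 0.168 | 0.138, 0.103 |

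**The outcome variables can stay.** If (follow-up − baseline) = a + b·arm + g·baseline, then follow-up = a + b·arm + (g + 1)·baseline. The arm effect b is the same, so ANCOVA on the difference equals ANCOVA on the follow-up value.

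**The case against.** The strongest objection is that covariates are normally left to a statistical analysis plan, which is not shown. The Protocol fixes outcome variables, not a model, and those variables already permit a baseline covariate. This stands to the extent that the absence of a stated model is not a fault and is not raised as one. It does not remove the suggestion, which attaches to six outcomes the Protocol defines by subtraction and on one of which it reports a between-arm result.

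Second, the gain rests wholly on two unknowns, and the range includes zero and a small loss. That also stands, so the gain is called possible and no more. The loss is bounded at about 1% of the SE.

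Third, results are already reported, so a second set of estimates could invite selection. This is fair. It is met by using one named model for all six outcomes and showing both sets.

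A reader might infer more than the document supports:
- *That the differences are biased or wrongly built.* Under randomisation the raw difference is unbiased.
- *That adjustment would change p = 0.0032 or the long-term conclusion.* The test is not named and no follow-up data are given, so neither can be re-derived. The Abstract's lack of an estimate or interval is a separate reporting matter, which an unadjusted interval would also answer.
- *That the statement "Data reflect the homogeneity of groups at the beginning of the study" is part of the problem.* No outcome analysis is said to depend on it, and balance at baseline neither creates nor removes the gain.
- *That the within-group p-values are affected.* The adjustment concerns only comparisons between arms.

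**Conclusion.** The point holds as an optional precision improvement. With equal SDs the SE would fall by between 1.4% (rho 0.9) and 18.5% (rho 0.3). With a follow-up SD 1.5 to 2 times baseline, the effect runs from about 1% worse to about 25% better, and it vanishes where the slope of follow-up on baseline is near 1. The document cannot say where in this range the trial lies. The figures assume 48 analysed participants and the same correlation and SD ratio in both arms. No error, bias or changed conclusion is claimed.

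**What to change.** Keep the six difference variables. Compare arms on each with one linear model (ANCOVA) containing arm and, as the only covariate, the participant's own PPTpre for the PPT outcomes or PIpre for the PI outcomes. Report the adjusted between-arm difference with its 95% CI beside the unadjusted difference and its CI for all six, whatever the results show. Label the adjusted set post hoc; it supplements the unadjusted comparison and does not replace it. If a statistical analysis plan already specifies this model, cite it and nothing further is needed.

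The cost is one re-run on data already collected, one degree of freedom per model and, at worst, an SE about 1% larger.

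### The conclusion that neither therapy is better in the long term is not supported by the results given: no between-arm estimate or interval is reported for day seven

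*Protocol*

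**What the plan says.** PPT and pain intensity (PI) are read before treatment and then three times: "A reassessment of PPT and PI was done on day one, three and seven post intervention" (Protocol, Material and Methods). Procedure section 6 turns each follow-up reading into its own change from the day-one pre-treatment value. For the immediate reading, "Variables PPTdiff1-1 and PIdiff1-1 were created based on differences" before and after treatment; the later variables are described as ones "that represented differences obtained between the measurements of days three and seven with those obtained on day one before intervention". No variable compares day seven with day three.

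The Abstract's Results give a p-value per visit within the experimental arm: "MEP demonstrated positive changes increasing PPT (PPTdiff1-1, p=0,0000, PPTdiff2-1, p=0,0000, PPTdiff3-1, p=0,0000" for PPT, and "decreasing PI (PIdiff1-1, p=0,0001, PIdiff2-1, p=0,0001, PIdiff3-1, p=0,0008) in experimental group" for PI. The only result that compares the arms is "significant differences in PPT at second reevaluation session compared to control group (PPTdiff2-1, p=0,0032". By the schedule, that is the day-three change in PPT.

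The Abstract's Conclusion calls microelectrolysis (MEP) a good analgesic treatment compared with ultrasound, and adds "although neither of two therapies seems to be better than other in long term". The last reading in the trial is day seven.

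**The concern.** The long-term clause is a statement about the difference between the arms at the end of follow-up. To support it, a reader needs the day-seven between-arm difference and its interval, and neither is reported. The within-arm p-values do not help, because they say nothing about the control arm.

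The likely basis is that the day-seven comparison did not reach significance. In a trial of this size a non-significant difference is compatible both with no effect and with a large one. Nor does a significant day three beside a non-significant day seven show that the effect changed between them; that requires the two arm differences to be compared directly, allowing for their correlation within participants.

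Duration of benefit is part of the headline conclusion. As worded, a reader may take it that the treatments are equivalent by day seven, or that the added benefit wears off within a week. Neither has been shown.

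**Working it through.** **Inputs from the Protocol.** Between-arm p = 0.0032 for the day-three PPT change (Abstract, Results). Arm sizes: "Working groups were designated as experimental (MEP group, n = 24) and control group (n = 24" (Procedure section 2).

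**Assumptions.** The test and significance level for the outcomes are not stated. I assume a two-sided two-sample t-test at 0.05 (Student's t is named only for Table 1), equal SDs of the change scores at the two visits, and a correlation rho between the day-three and day-seven changes, varied from 0.3 to 0.9. Differences are in SD units of the change score.

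**Step 1. The plan's own figure.** No follow-up means or SDs are given, so p = 0.0032 cannot be reproduced; it can only be inverted.
- df = 24 + 24 − 2 = 46; two-sided p = 0.0032 gives t = 3.11.
- d3 = t × √(2/24) = 3.11 × 0.2887 = 0.90 SD.
- Approximate 95% CI: 0.90 ± 2.013 × 0.2887 = 0.32 to 1.48 SD.

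**Step 2. What a non-significant day seven could mean.**
- Smallest significant observed difference = 2.013 × 0.2887 = 0.58 SD. The 95% half-width is the same 0.58 SD.
- Power at a true difference of 0.5 SD is about 41% (normal approximation); 80% power needs about 0.81 SD.
- An observed 0.40 SD at day seven would have p = 0.17 and a 95% CI of 0.40 ± 0.58 = −0.18 to 0.98, which contains both zero and the day-three estimate of 0.90.

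**Step 3. Could the effect have faded?** The contrast is t = (d3 − d7) / [0.2887 × √(2(1 − rho))] on 46 df. Its standard error is 0.342, 0.289, 0.224 and 0.129 SD at rho 0.3, 0.5, 0.7 and 0.9.

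| Assumed day-seven estimate (SD) | Day-seven p | Contrast p, rho 0.3 | rho 0.5 | rho 0.7 | rho 0.9 |
|---|---|---|---|---|---|
| 0.576 | 0.052 | 0.35 | 0.27 | 0.16 | 0.016 |
| 0.40 | 0.17 | 0.15 | 0.09 | 0.03 | <0.001 |
| 0.30 | 0.30 | 0.087 | 0.044 | 0.010 | <0.001 |
| 0.20 | 0.49 | 0.047 | 0.020 | 0.003 | <0.001 |

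Every row is non-significant at day seven, yet the contrast runs from no evidence of fading to strong evidence of it. The document supplies neither the day-seven estimate nor rho, so it does not say which cell applies.

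**Step 4. How often a constant effect gives this pattern.** Simulation with the same true effect at all three visits (20,000 trials per setting): at 0.5 SD, given a significant day three, day seven was non-significant in 30% of trials at rho 0.7 and in 49% at rho 0.3. At a true 0.9 SD the figures were 8% and 11%. The pattern is common without fading when the true effect is moderate, and uncommon when it is large.

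**Step 5. Day three.** Bonferroni over three visits gives 3 × 0.0032 = 0.0096; over two outcomes and three visits, 6 × 0.0032 = 0.019.

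**The case against.** The strongest reply is that the Abstract makes a hedged statement about the later time point and never says that the effect was present at day three and then vanished. That is right. A reader might infer a claim of fading, since the clause qualifies a favourable verdict, but the document does not state one. The main weakness is therefore that absence of a significant difference is treated as absence of a difference; the missing contrast matters only for the inferred reading.

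Second, the day-seven non-significance is itself inferred, since no between-arm result for that visit is printed. A statistical analysis plan may exist, so one cannot say that a repeated-measures analysis was never done, only that none is described or reported here. This also stands, and the point does not rest on a missing analysis section: a conclusion is stated here and the results stated here do not carry it.

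Third, fading may be real. It would be wrong to say that only a day-seven estimate near zero could show it: 0.30 SD gives a contrast p of 0.010 at rho 0.7, and at rho 0.9 even 0.576 SD gives 0.016. Because all changes share one baseline, equal variances and equal correlations among the readings imply rho = 0.5, so 0.3 is at the pessimistic end.

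Fourth, separate changes from baseline at each visit are legitimate outcomes and are declared as such. Analysing them visit by visit is not in itself an error.

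**Conclusion.** The point holds for the long-term clause. With one between-arm result reported, at day three, and nothing for the immediate or day-seven readings, the document supports neither similarity of the arms at day seven nor a loss of effect by then. At 24 per arm a day-seven estimate carries an uncertainty of about ±0.58 SD, against a day-three estimate of about 0.90 SD. Both figures rest on the assumed two-sided t-test, and the contrast p-values also on equal SDs and an assumed correlation.

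Two stronger readings are not supported. One is that the clause is false: it is unsupported, and the data may yet bear out fading. The other is that the day-three finding is in doubt: nothing here undermines it, and it survives a Bonferroni adjustment over six tests.

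This should be corrected, because it changes what the trial may say about duration of benefit.

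**What to change.** 1. For each outcome (PPT and PI), fit one repeated-measures model to the immediate, day-three and day-seven readings, with arm, visit, arm-by-visit and within-person correlation, adjusted for the pre-treatment value.
2. Report the between-arm difference with its 95% CI at all three readings, whether or not it is significant.
3. Replace the long-term clause with a statement that names day seven and follows from that visit's interval. If the interval is wide, call the day-seven comparison inconclusive.
4. State that the benefit fades only if the day-three minus day-seven contrast supports it. Do not use that contrast to justify saying that the arms are alike at day seven: at 0.40 SD and rho 0.7 the contrast has p = 0.03, while the day-seven interval still runs from −0.18 to 0.98 SD.

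The cost is a small re-analysis of existing data and a reworded sentence, with no new measurements. The downside is a less definite conclusion.
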